3.3.1 Baseline Screening & Enrollment (Visit 1)

Eligible study participants will be screened, approached, and consented for the study. The screening and enrollment process may be performed remotely via telephone prior to the procedure date, or performed in the pre-procedure area on the day of procedure. Relevant study material will be provided to the patient at this time.

3.3.2 Clinical Procedure/Accrual (Visit 2)

The devices will be secured to the wrist and torso by study staff prior to administration of sedatives. The devices will be programmed to record respiratory rate, heart rate, oximetry, skin temperature as well as single-lead ECG. The patient will undergo his or her scheduled procedure. On completion of the procedure, the devices will be removed by the study staff will download data onto a central device for analysis.

3.3.3 Survey (Visit 3)

The day after the patient's procedure, a survey will be submitted to them electronically which will remain open until 14 days after the procedure. An electronic reminder will be sent if uncompleted at 7 days, followed by a telephone reminder if not completed at 13 days. There will be no additional patient follow up after completion of the survey. At study completion, a survey will be sent to involved proceduralists and anesthetists. will be provided electronically to patients to assess their satisfaction and opinions regarding their experience.

3.4 Primary Safety Endpoints

There are no specific primary safety endpoints pertaining to the study given the non-invasive intervention. Wearable technology like smart watches and smart phones are already permitted within the procedural area.

4 Subject Selection, Enrollment and Withdrawal

All patients who are undergoing gastrointestinal endoscopic procedures with sedation may be eligible for the study. It is anticipated that we will screen up to 1000 subjects and enroll 500 subjects to the study.

4.1 Inclusion Criteria

1. Adults over 18 years of age
2. Undergoing gastrointestinal endoscopic procedures with sedation
3. Able to give appropriate consent to the study or have an appropriate representative to do so.

4.2 Exclusion Criteria

1. Pregnancy
2. Physical deformity, wound, or dressing preventing placement of a wearable device on the wrist or torso
3. Allergy to aluminum, nickel or acrylate

4.3 Subject Recruitment, Enrollment and Screening

Potential study subjects will be screened, recruited and enrolled by the principal and co-investigators, along with trained research personnel who are able to gain consent. Relevant material regarding the study will be handed to the subject for review.

4.4 Early Withdrawal of Subjects

4.4.1 When and how to Withdraw Subjects

The subjects will undergo the clinically indicated procedure with the wearable devices. Early withdrawal would include removal of the devices prior to procedure completion, which can be performed at the discretion of the patient or clinical providers at any point.

4.4.2 Data Collection and Follow-up for Withdrawn Subjects

Withdrawn subjects will be recorded in the study record in order to calculate the withdrawal rate. There will be no further utilization of any subject related data.

5 Statistical Plan

5.1 Sample Size Determination

Power analysis not performed as this study is descriptive and we do not plan to perform any statistical testing.

5.2 Statistical Methods

Descriptive Statistics

Baseline values for demographic, clinical, and outcome will be tabulated for the study subjects. Continuous variables will be expressed as mean and standard deviation. Categorical variables will be expressed as percentages.

We will measure the rate of concordance between device detection and documentation in anesthesia record (# of events recorded on wearable device / events noted on anesthesia record). Events to be recorded include tachycardia (HR > 100), bradycardia (HR < 60), desaturation (peripheral O₂ saturation < 88%), any arrhythmia, and tachypnea (RR > 18).

We will also calculate the difference in maximum and minimum heart rate, respiratory rate, and oxygen saturation recorded by the watch compared to the sedation record.

Handling of Missing Data

Subjects with missing or incomplete data will be noted but will not include in the final analysis. Available information regarding these patients will be reported separately to allow for evaluation of external validity

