5.3 SUBJECT POPULATION(S) FOR ANALYSIS	12
6 SAFETY AND ADVERSE EVENTS	12
7 DATA HANDLING AND RECORD KEEPING	13
7.1 CONFIDENTIALITY.....	13
7.2 SOURCE DOCUMENTS.....	13
7.3 RECORDS RETENTION	14
8 STUDY MONITORING, AUDITING, AND INSPECTING	14
8.1 STUDY MONITORING PLAN	14
8.2 AUDITING AND INSPECTING	15
9 ETHICAL CONSIDERATIONS.....	15
10 STUDY FINANCES	15
10.1 FUNDING SOURCE	15
11 PUBLICATION PLAN	15

12	REFERENCES	15
13	ATTACHMENTS	ERROR! BOOKMARK NOT DEFINED.

LIST OF ABBREVIATIONS

CFR	Code of Federal Regulations
CRF	Case Report Form
DSMB	Data and Safety Monitoring Board
FDA	Food and Drug Administration
GCP	Good Clinical Practice
HIPAA	Health Insurance Portability and Accountability Act
IRB	Institutional Review Board
PHI	Protected Health Information
PI	Principal Investigator
SAE	Serious Adverse Event/Serious Adverse Experience
SOE	Schedule of Events
SOP	Standard Operating Procedure
IQR/M	Interquartile Range/Median

Study Summary

Title	A Prospective Study of the Role and Accuracy of Consumer-Facing Wearable Technology for Patient Monitoring in Gastrointestinal Endoscopy
Running Title	Wearable Technology Endoscopy
Title Acronym	Wearable Tech
IRB Protocol Number	21-007738
Phase	Prospective study
Methodology	Subjects who are eligible will have two consumer-facing wearable smart devices placed before scheduled endoscopy. Data from the devices will be downloaded after the procedure and analyzed. Patients and providers will complete a survey regarding their experience.
Overall Study Duration	6 months Recruitment and Active study execution, 3 months analysis and 3 months publication. Total: 12 months
Subject Participation Duration	Up to 60 days screening prior to study procedure, duration of the procedure itself, and completion of a survey within 14 days of procedure date
Objectives	Measure the accuracy and safety of wearable technology in patients undergoing endoscopic gastrointestinal procedures with sedation. Assess patient and provider preferences regarding wearable technology.
Number of Subjects	Five hundred (500)
Diagnosis and Main Inclusion Criteria	Subjects over 18 years of age who are scheduled to undergo an endoscopic procedure with sedation
Study Device	Consumer-facing wearable smart devices(examples include Apple Watch Series 6, FitBit Versa, The QardioCore ECG ambulatory monitoring device)
Reference Modality	Sedation/Anesthesia record

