Statistical Methodology	All continuous variables will be expressed as mean and standard deviation. Categorical variables will be expressed as percentages.

1 Introduction

This document is a clinical research protocol relating to a prospective study of the role and accuracy of consumer-facing wearable technology in gastrointestinal endoscopy. The described study will be conducted in compliance with this protocol, applicable United States government regulations and Mayo Clinic policies and procedures.

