1.4 Study Rationale and Risk Analysis (Risks to Benefits Ratio)

1.4.1 Study Rationale

We hope to further characterize and define the role of consumer-facing technology in the clinical environment by focusing on device accuracy when compared to standard clinical monitoring in patients undergoing an endoscopic procedure. We will generate and answer questions related to these devices that have not yet been explored in the gastroenterology literature. We will provide a timely and much-needed framework that addresses both practical and theoretical considerations around a technology that has become increasingly relevant to patients.

This study will specifically address whether consumer facing wearable devices can serve as patient monitoring devices in a comparable manner to the current gold standard in the procedural suite. In addition to accuracy, we will assess whether certain procedural maneuvers interfere with device data collection. This information will be relevant to patients, providers and healthcare institutions and can help inform policy regarding these devices.

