2.1 Primary Objective

Measure the accuracy of wearable technology for patient monitoring compared to currently used equipment in patients undergoing gastrointestinal endoscopic procedures with sedation

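### Mean and SD are the only planned summaries for the differences in maximum and minimum heart rate and respiratory rate, so a small share of artefact readings can inflate the SD and hide both typical spread and gross errors

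*Combined protocol and SAP*

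**What the plan says.** The primary objective (section 2.1) is accuracy against current equipment: "Measure the accuracy of wearable technology for patient monitoring compared to currently used equipment in patients undergoing gastrointestinal endoscopic procedures with sedation". Section 5.2 gives two measures of it.

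- An event measure: "We will measure the rate of concordance between device detection and documentation in anesthesia record", based on fixed thresholds.
- A continuous measure, with the sedation record as reference: "We will also calculate the difference in maximum and minimum heart rate, respiratory rate, and oxygen saturation recorded by the watch compared to the sedation".

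The only rule for summarising continuous data is "Continuous variables will be expressed as mean and standard deviation" in section 5.2. The Study Summary, under statistical methodology, is broader: "All continuous variables will be expressed as mean and standard deviation". The statistical plan contains no median, percentile, range, limits of agreement, percentage within a tolerance, or rule for artefact. The abbreviation list has an entry for "Interquartile Range/Median", but the plan does not use it.

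On exclusions, section 5.2 says "Subjects with missing or incomplete data will be noted but will not include in the final analysis", and section 5.3 analyses everyone who wore the device throughout the procedure. Neither deals with a reading that was recorded but is false. Section 1.4.1 expects that disturbance is possible: "we will assess whether certain procedural maneuvers interfere with device data collection".

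**The concern.** A per-patient maximum or minimum is the most deviant reading in the trace. If one reading is false and extreme, it becomes that patient's value, and nothing in the plan removes or flags it. The SD depends on squared deviations, so a few such patients can supply most of it.

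A watch that is close in nearly all patients and grossly wrong in a few can then produce the same mean and SD as a watch that is moderately imprecise in everyone. These two devices have different implications for the uses named in section 1.4.3: monitoring where standard equipment is lacking, and awareness of inaccurate readings. Section 5.1 plans no testing, so the descriptive summaries are the whole result. The event measure does not fill the gap, because it counts threshold crossings and says nothing about the size of an error.

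**Working it through.** The documents state no SD, bias, artefact rate or artefact size, so there is no planned figure to reproduce. The check is an illustration on assumed values. From the documents: 500 patients, and mean and SD as the only summary. Assumed: clean differences in maximum heart rate are Normal with mean 0 and SD s; a share p of patients has the difference shifted by A bpm.

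**Formulas.** Mean = pA. Variance = s² + p(1-p)A². Median and quartiles come from the mixture distribution.

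**Main case: s = 4, A = 50, p = 0.02 (10 of 500).**
- Mean = 0.02 × 50 = 1.0.
- Variance = 16 + 2500 × 0.02 × 0.98 = 65, so SD = 8.06, double the clean value.
- Mean ± 1.96 SD = 1.0 ± 15.8 = -14.8 to +16.8.
- Median 0.1; IQR -2.6 to +2.9.

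**What a reader would infer from mean 1.0 and SD 8.06, assuming normality, against the mixture itself.**

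| Quantity | Inferred | In the mixture |
|---|---|---|
| IQR | 1.0 ± 0.6745 × 8.06 = -4.4 to +6.4 | -2.6 to +2.9 |
| Within 5 bpm | 46% | 0.98 × 78.9% = 77% |
| Error above 30 bpm | about 0.02% | 2% |

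The SD overstates the typical spread and understates the gross errors.

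**Sensitivity to the assumptions, with s = 4.**

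| Share affected | Shift | Mean | Variance | SD |
|---|---|---|---|---|
| 0.4% (2 of 500) | +50 | 0.2 | 16 + 2500 × 0.004 × 0.996 = 25.96 | 5.1 |
| 2% (10 of 500) | +20 | 0.4 | 16 + 400 × 0.0196 = 23.84 | 4.9 |
| 2% (10 of 500) | +50 | 1.0 | 65 | 8.1 |
| 5% (25 of 500) | +50 | 2.5 | 16 + 2500 × 0.0475 = 134.75 | 11.6 |

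At 5% and +50 bpm the median is still 0.3.

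**A second set of assumptions, with s = 5.** Five patients of 500 at +80 bpm give mean 0.8 and SD √(25 + 6400 × 0.0099) = 9.4, with 72% of the variance from artefact. At +40 bpm the same five give mean 0.4 and SD 6.4. Twenty-five patients at +80 bpm give mean 4.0 and SD 18.1, against a median of 0.3.

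**How a rare artefact reaches the extreme.** If each reading is false with probability q, independently, a patient with n readings has at least one false reading with probability 1 - (1-q)ⁿ. With q = 0.1% (assumed) this is 1.0%, 3.0% and 9.5% for 10, 30 and 100 readings.

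No calculation was made for respiratory rate. The same mechanism applies, but its size is not quantified here.

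**The case against.** **The mean is not much affected.** A reader might infer that the reported bias is as misleading as the spread, so that a watch accurate in 98% of patients would look wrong in everyone. The figures do not support this. At 2% and +50 bpm the mean exceeds the median by only 0.9 bpm, and in the scenarios with 2 to 5 affected patients in 500 the mean moves by less than 1 bpm. It shifts by 2 bpm or more only at about 5% affected. This objection stands.

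**The artefact is assumed.** A reader might also take it as given that these differences will be heavy-tailed. The documents do not show this. Section 3.1 says that readings come from the watch's native applications but not whether these already filter the signal, and section 1.4.1 only plans to look for interference. Without artefact, mean and SD serve well for near-symmetric differences. This stands too: the SD can be inflated, but it need not be.

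**The rule may not apply to the differences.** In section 5.2 the mean-and-SD sentence follows one on baseline tabulation, and the sentence on differences names no summary. But the baseline sentence also names outcomes, and the Study Summary says all continuous variables. The reading is reasonable, though inferred.

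**The unused abbreviation.** A reader might see the median and IQR entry as evidence of a dropped analysis. It may equally be template residue, and nothing here rests on it.

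**The summaries can be added later.** The study is exploratory and the data are kept, so nothing is lost for good. But a tolerance band or gross-error limit chosen after the outliers are seen carries less weight than one fixed beforehand.

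**There is a larger problem with extremes.** In a simulation with independent readings (SD 8 bpm), an error-free watch with 60 readings exceeds a record with 6 by about 8.5 bpm in the maximum. That bias would shift the median too. It is a separate issue: robust summaries do not cure it, and it does not remove the need for them.

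**Conclusion.** The point holds as a possibility that the plan does not guard against. With mean and SD alone, and no artefact rule, a small share of gross errors can inflate the SD of the heart-rate and respiratory-rate differences until it describes neither the typical spread nor the tail. The mean stays close to typical performance unless about 5% or more of patients are affected.

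For heart rate the effect ranges from slight (SD 4.9 against 4.0 for 2% at +20 bpm) to a doubling (8.1 for 2% at +50 bpm) or more (11.6 for 5% at +50 bpm). Which applies depends on artefact frequency and size, both assumed here. The conclusion also rests on reading the general mean-and-SD rule as covering the differences. This is a reporting weakness worth correcting before analysis. It does not show that the results will be wrong.

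**What to change.** In section 5.2, state that each difference in maximum and minimum heart rate and respiratory rate will be reported with the following, beside the mean and SD:

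- median and IQR;
- full range;
- percentage of patients within a pre-set band;
- number of patients beyond a pre-set gross-error limit;
- a plot of the distribution.

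The sponsor should choose the band and the limit and record them before analysis. Align the statistical methodology entry in the Study Summary.

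The range and the gross-error count are needed because outer percentiles alone can miss the tail: in the 2% case at +50 bpm the 2.5th and 97.5th percentiles are -7.8 and +10.3, and the errors near 50 bpm lie outside them.

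The cost is SAP wording and a longer table, with no new data. The change does not correct bias from different sampling rates of watch and record, which must be handled separately.

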1.4.3 Potential Benefits

If successful and reliable, the use of mass-produced consumer devices could be used in locations where traditional cardiopulmonary monitoring devices are unavailable. Alternatively, inaccurate device readings would have medicolegal implications of which patients, providers and healthcare systems should be aware. This information can help inform institutional policy.

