3.1 General Design

We will perform a prospective, non-blinded, exploratory study to assess the accuracy and safety of smart technology in the endoscopy suite for patients undergoing gastrointestinal endoscopic procedures with sedation. We will also simultaneously perform an assessment of patient and provider preferences using narrative-driven, qualitative evaluation.

Patients will be identified by reviewing daily procedure listings on endoscopy units on Alfred 6, Gonda 2 and Gonda 9. Recruitment will occur over the phone the day prior to a procedure, or the pre-procedure areas on the day of the procedure. Patients who meet inclusion criteria and consent to participation in the study will be provided the smart devices. The devices will be secured to the wrist and torso by study personnel prior to administration of sedatives. The smart watch will be programmed to record respiratory rate, heart rate, and oximetry using native, first party device applications. These applications include *Blood Oxygen* (measures oxygen saturation), *ECG* (records single lead ECG), *Heart Rate* (heart rate), and *Health* (which logs respiratory rate while sleeping). The QardioCore ECG device will measure a single-lead ECG, heart rate, skin temperature, and respiratory rate.

The patient will undergo his or her scheduled procedure. Patients, proceduralists and anesthetists will not be blinded to their enrollment as the devices will be visible. On completion of the procedure, the devices will be removed by the study coordinator and data downloaded onto a central device for analysis. Procedural information will be extracted from the operative note, sedation record, and anesthesia encounter in EPIC. The day after the patient's procedure, a survey will be submitted to them electronically which will remain open until 14 days after

the procedure. Aen electronic reminder will be sent if uncompleted at 7 days, followed by a telephone reminder if not completed at 13 days. There will be no additional patient follow up after completion of the survey. At study completion, a survey will be sent to involved proceduralists and anesthetists.

3.2

Figure 1: Study Design

[figure not shown]

Table 1. Schedule of Events

	Baseline Screening & Enrollment Visit 1 Days -60 to 0	Accrual: Study Intervention Visit 2 Day 0	Patient Survey Visit 3 Day +1 to +14	Provider survey Days 0 to 180
Inclusion/ Exclusion	X	X (if not performed earlier)		
Device(s) Placement/ Recording		X		
Patient Survey			X	

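### The event concordance rate in 5.2 is an unmatched count ratio at fixed cut-offs, so it shifts with how many patients lie near the line and cannot show whether clearly abnormal values are missed

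*Combined protocol and SAP*

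**What the plan says.** Section 5.2 states: "We will measure the rate of concordance between device detection and documentation in anesthesia record". It defines the rate as the number "of events recorded on wearable device / events noted on anesthesia record". The events are "tachycardia (HR > 100), bradycardia (HR < 60"), desaturation ("saturation < 88"%) and "any arrhythmia, and tachypnea (RR > 18"). Four of the five are therefore a threshold on a measured value. Arrhythmia has no numeric threshold.

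The section gives no rule for pairing a device event with a record event, and no severity tier, tolerance or duration. It does not say whether the count is per patient or per episode.

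It adds a second analysis: "We will also calculate the difference in maximum and minimum heart rate, respiratory rate, and oxygen saturation recorded by the watch", compared with the sedation record. Under the general rule in the same section, continuous variables are summarised as mean and SD.

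Accuracy is the primary objective (2.1). Section 1.4.1 asks whether wearables can monitor patients comparably to the current standard. Section 1.4.3 says that, if reliable, such devices "could be used in locations where traditional cardiopulmonary monitoring devices are unavailable".

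**The concern.** A record heart rate of 59 and one of 40 each add one event to the denominator. If the watch reads 60 in both cases, neither adds to the numerator. If the watch reads 59 in another patient whose record value is 60, the numerator gains an event that restores the balance. The ratio therefore mixes three things: device error, the number of patients close to the cut-off, and the cancelling of misses by false alarms.

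Whether a wearable could stand in for a monitor depends mainly on whether clearly abnormal values go undetected. The ratio does not show that. The maximum/minimum differences have no cut-off and do reflect size. However, averaged over all subjects, a few large disagreements among patients with events can be diluted by many small ones among patients without.

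**Working it through.** The plan has no figure to reproduce. Section 5.1 reports no power analysis, and the documents state no target concordance, device error or vital-sign distribution. What follows is an illustration for bradycardia.

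**Inputs.** The cut-off of 60 is from 5.2. Everything else is assumed: lowest record heart rate T ~ N(μ, 9), with μ = 62 as base and 55 and 70 as alternatives; device value D = T + N(0, e), with e = 3 as base and 2 and 5 as alternatives; one value per patient, and always a reading unless stated.

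**Formulas.**
- Planned ratio: P(D<60)/P(T<60) = Φ((60−μ)/√(81+e²)) / Φ((60−μ)/9).
- Matched misses: P(T<60 and D≥60)/P(T<60), integrating the normal density of T times 1−Φ((60−t)/e) over t<60.
- Far misses (events more than 5 bpm beyond the line): P(T<55 and D≥60)/P(T<55).

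**Same device (e = 3), different populations.**

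| μ | P(T<60) | P(D<60) | Planned ratio | Matched misses | Far misses |
|---|---|---|---|---|---|
| 55 | 0.7107 | 0.7009 | 0.986 | 6.9% | 0.5% |
| 62 | 0.4121 | 0.4165 | 1.011 | 11.6% | 0.8% |
| 70 | 0.1333 | 0.1459 | 1.095 | 16.9% | 1.1% |

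At μ = 62 the cancelling is visible. Misses are 0.0478 of all patients (0.0478/0.4121 = 11.6%) and false alarms are 0.0523. Then 0.4121 − 0.0478 + 0.0523 = 0.4166, which is P(D<60) up to rounding.

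**Different error, μ = 62.**

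| e | Planned ratio | Matched misses | Misses within 2 bpm of 60 | Misses within 5 bpm |
|---|---|---|---|---|
| 2 | 1.005 | 8.0% | 81% | 99.6% |
| 3 | 1.011 | 11.6% | 65% | 96% |
| 5 | 1.027 | 17.9% | 48% | 85% |

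The ratio rises as the device gets noisier. With P(T<55) = Φ(−7/9) = 0.2184, far misses at e = 5 are 0.179 × 0.149 × 0.4121/0.2184 = 5.0%, against 0.8% at e = 3. The ratio moves only from 1.011 to 1.027.

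**Reading gaps.** Suppose the device gives no reading 10% of the time, at random, with μ = 62 and e = 3:
- Ratio: 0.9 × 1.011 = 0.91.
- Matched misses: 0.9 × 11.6% + 10% = 20.4%.
- Far misses: 0.9 × 0.8% + 10% = 10.7%.
- Share of misses within 5 bpm: (0.9 × 0.0478 × 0.963 + 0.1 × (0.4121 − 0.2184))/(0.204 × 0.4121) = about 72%.

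**Two cases the ratio cannot tell apart (e = 3).** With μ = 55 and no gaps, the ratio is 0.986 and far misses are 0.5%. With μ = 70 and 10% gaps, the ratio is 0.9 × 1.095 = 0.986 and far misses are 0.9 × 1.1% + 10% = 11.0%.

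**Pairing alone is not enough.** A noiseless device that drops 11.6% of readings at random has the same overall matched misses as the e = 3 device at μ = 62. It misses 11.6% of far events instead of 0.8%. Only the split by distance separates the two.

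**The other numeric events.** By simulation with whole-unit values, error SD 2, no gaps and assumed normal extremes:

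| Event | Assumed mean, SD | Planned ratio | Matched detection | Detection more than 5 units beyond |
|---|---|---|---|---|
| HR > 100 | 90, 15 | 1.009 | 93.7% | 100.0% |
| SpO2 < 88% | 94, 4 | 1.41 | 75.2% | 99.8% |
| RR > 18 | 18, 4 | 1.012 | 84.6% | 99.9% |

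For SpO2, near-line false alarms outnumber misses, so the ratio exceeds 1 by a wide margin while a quarter of events are missed.

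**The case against.** The strongest reply is that the study is exploratory (3.1) and descriptive with no testing (5.1), sets no acceptance threshold, and mentions wider use only conditionally in 1.4.3. The maximum/minimum differences already show size: a record minimum of 40 against a watch minimum of 60 gives a 20 bpm difference. Banding could be done from the same data at reporting. All of this stands, and it limits the point to analysis and reporting. It does not remove the point, because those differences are not linked to events and a band width chosen after seeing the data is weaker than one fixed beforehand.

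A reader might go further and infer that most misses by a good device lie one or two units from the line. The documents do not support that. They give no device error, and under the assumptions above the share within 2 bpm falls from 81% to 48% as error SD goes from 2 to 5. Reading gaps lower it further. Gaps are plausible: 3.1 describes the watch's respiratory-rate application as one "which logs respiratory rate while sleeping", and 1.4.1 plans to look for interference from procedural maneuvers. Section 5.2 excludes subjects with incomplete data but does not say whether an intermittent gap counts as incomplete.

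A reader might also take the 11.6% as what the plan would report. It would not: the written ratio does not identify individual misses and would read about 1.01.

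**Conclusion.** The point holds as a minor but specific gap. For the four numeric event types, the concordance rate is unmatched and takes no account of distance from the cut-off. The same device can score 0.99 or 1.10 depending on the population, while its misses among events more than 5 bpm beyond the line stay near 1%. Conversely, the same ratio can go with far misses of 0.5% or 11.0%.

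The structural finding rests on the wording of 5.2 alone. The sizes rest on assumed normal distributions, unbiased independent error and one value per patient, and should be read only as illustration. Larger error or reading gaps lower the near-line share of misses and raise the far share, which makes the far band more informative. Arrhythmia is outside the cut-off argument, although its count is unmatched too.

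**What to change.** In 5.2:

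- Pair device and record values by patient and event.
- For the four numeric event types, report detection in two bands of the record value: near the cut-off and clearly beyond it. Fix the widths for heart rate, SpO2 and respiratory rate before analysis.
- Show these results beside the planned maximum/minimum differences, and base any statement about suitability for monitoring on the band clearly beyond.
- Report arrhythmia unbanded. The event cut-offs stay as they are.

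No new measurements are needed. The costs are the pairing work, which is more than one extra table split, and fewer events per cell in the far band.

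### The event concordance rate in section 5.2 lets device-only events cancel missed ones, or leaves them out, so it cannot measure accuracy

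*Combined protocol and SAP*

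**What the plan says.** The primary objective (section 2.1) is to "Measure the accuracy of wearable technology for patient monitoring compared to currently used equipment". The rationale (section 1.4.1) asks whether wearables "can serve as patient monitoring devices in a comparable manner to the current gold standard". The Study Summary names the sedation/anesthesia record as the reference.

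Section 5.2 plans two accuracy analyses.

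- **Event detection.** "We will measure the rate of concordance between device detection and documentation in anesthesia record", defined as the number "of events recorded on wearable device / events noted on anesthesia record". "Events to be recorded include tachycardia (HR > 100), bradycardia (HR < 60), desaturation" (oxygen saturation below 88%), any arrhythmia, and a respiratory rate above 18.
- **Extremes.** The "difference in maximum and minimum heart rate, respiratory rate, and oxygen saturation recorded by the watch compared to the sedation record".

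Nothing in the document says how a device event is matched to a record event by patient, type or time, what counts as one event, or how counts are combined over patients. No 2x2 table, sensitivity, specificity, PPV or count of device-only events is planned.

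Two devices are worn. Besides the watch there is a torso device, and section 3.1 states: "The QardioCore ECG device will measure a single-lead ECG, heart rate, skin temperature, and respiratory rate".

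**The concern.** An accuracy measure has to separate three things: events that both sources show, events only the record shows (missed), and events only the device shows (device-only, that is, false alarms if the record is taken as the truth). The formula in 5.2 has one total over another and does not separate them. A figure near 100% could come from a device that finds every event, or from one that misses half and raises as many events that the record does not show.

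The word concordance also permits a second reading, in which the numerator counts only record events that the device also detected. Device-only events then drop out of the report altogether.

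The study plans no hypothesis test, so its descriptive estimates are the whole result. Section 1.4.3 foresees use of the findings where conventional monitors are unavailable, and in institutional policy. For both purposes, the reader needs to know how often the device misses events and how often it raises events that the record lacks.

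**Working it through.** The plan states no expected concordance, event frequency or power, so there is no figure of its own to reproduce. From the documents come the formula (5.2) and N = 500 (section 4). All event counts below are assumed.

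**Notation.** TP = record events matched by the device; FN = record events missed; FP = device-only events; TN = patients with the event on neither source. R = TP + FN is the number of record events. Sensitivity = TP/R; PPV = TP/(TP + FP); specificity = TN/(TN + FP).

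**1. Literal reading, counts pooled over patients.**

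Ratio = (TP + FP)/(TP + FN) = sensitivity + FP/R. When TP > 0 this equals sensitivity/PPV.

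The ratio is 100% whenever FP = FN, and it has no upper limit. With R = 100:

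| Matched | Missed | Device-only | Ratio | Sensitivity | PPV |
|---|---|---|---|---|---|
| 80 | 20 | 20 | 100% | 80% | 80% |
| 50 | 50 | 50 | 100% | 50% | 50% |
| 0 | 100 | 100 | 100% | 0% | 0% |
| 90 | 10 | 60 | 150% | 90% | 60% |

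**2. The same reading at patient level.** Take N = 500 with 50 patients positive on the record (10%, assumed).

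- Perfect device, TP/FN/FP/TN = 50/0/0/450: ratio 50/50 = 100%.
- Poor device, 25/25/25/425: ratio (25 + 25)/50 = 100%. Sensitivity and PPV are each 25/50 = 50% (exact 95% CI 35.5% to 64.5%), and specificity is 425/450 = 94.4% (91.9% to 96.4%).

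**3. A device unrelated to the record.** The ratio is then roughly the device's flag rate over the record's rate. In a simulation (4,000 replicates, N = 500, record rate 10%), flag rates of 5%, 10% and 20% gave mean ratios of 0.51, 1.02 and 2.04. PPV was 0.10 throughout. Such a device scores near 100% only when the two rates are about equal.

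**4. Matched reading.** Ratio = TP/R = sensitivity. FP does not enter. With 45 of 50 detected, the measure is 90% (78.2% to 96.7%) in both of these cases:

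| TP/FN/FP/TN | Matched ratio | Literal ratio | PPV | Specificity |
|---|---|---|---|---|
| 45/5/5/445 | 90% | 50/50 = 100% | 45/50 = 90% | 445/450 = 98.9% |
| 45/5/90/360 | 90% | 135/50 = 270% | 45/135 = 33.3% (25.5% to 42.0%) | 360/450 = 80.0% (76.0% to 83.6%) |

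The second row also shows that the two readings can give 90% and 270% from the same data. The text does not say which one applies.

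**5. Does the other planned analysis fill the gap?** The differences in extremes are specified for the watch only, and for heart rate, respiratory rate and oxygen saturation only. The two extremes being compared need not occur at the same time, and the differences give no count of missed or device-only events. The torso device, and arrhythmia on either device, have no planned accuracy measure except the ratio.

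**The case against.** The strongest reply is that concordance between detection and documentation most naturally means documented events that the device also found, with the formula as shorthand. On that reading nothing offsets anything, the value cannot exceed 100%, and sensitivity is a legitimate half of the answer. This is fair, but it moves the defect rather than removing it: device-only events are then reported nowhere.

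Second, four of the five event types are threshold crossings of an extreme. A watch that misreads extremes in both directions would tend to show a wide standard deviation in the planned differences, even if the mean were near zero. This stands for the watch, and it limits the damage there. It does not reach the torso device or arrhythmia.

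Third, the reference is a charted record, so a device-only event may be a real event that nobody charted. This also stands and affects the wording of results: such events should be labelled device-only, not presumed to be device error. It is a further reason to count them separately.

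Fourth, the study is exploratory and descriptive, and every size given here rests on assumed counts. Section 5.1 does excuse the absence of power and testing. It does not excuse a descriptive statistic that fails to describe agreement, and the algebra needs no assumed frequency.

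Finally, a patient-level table has a limit of its own: an event at one time on the device and at another on the record counts as agreement. Event-level matching is therefore worth adding where timestamps permit.

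**Conclusion.** The concern holds, and 5.2 must be changed. As printed, the ratio equals sensitivity plus device-only events per record event, so 100% does not imply agreement: half the events can be missed and the score is still 100%. On the kinder reading it is sensitivity alone, and PPV can range from 90% to 33.3% behind the same reported 90%.

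The literal result assumes that counts are pooled over patients, which the plan does not specify. The numerical examples assume 100 record events, or 50 record-positive patients among 500. The gap is widest for the torso device and for arrhythmia, where no other accuracy analysis is planned. For the watch's heart rate, respiratory rate and saturation, the differences in extremes offer partial protection.

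**What to change.** Replace the ratio in section 5.2 with text such as:

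> For each device and each event type separately, a patient-level 2x2 table (event yes/no on the device against yes/no on the anesthesia record) will be reported, with sensitivity, specificity and PPV and exact 95% confidence intervals. Events seen only by the device will be reported as device-only. The two devices will not be combined in one numerator.

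This needs no time matching. Where both sources carry usable timestamps, add event-level sensitivity and PPV with a counting unit and matching window fixed before analysis, and patient-clustered bootstrap intervals. The window could be plus or minus one charting interval of the record; the documents do not give that interval, so the study team would have to supply it. Note in the reporting that some device-only events may be true but uncharted. Keep the maximum and minimum differences as a complementary analysis.

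The cost is a wording change and some extra analysis of data already to be collected, with no extra patients or procedures. The reported figures may look less favorable than the unmatched ratio would.
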